10 CHAPTER 7: STATISTICAL CONSIDERATIONS

10.1. Study Design

This open-label trial involves one primary and several secondary objectives. Post-transplant HCV status will be monitored, and patients will be treated with 12-16 weeks of therapy with Zepatier, Epclusa, or another appropriate antiviral treatment, after which time, treatment will be complete, barring instances of treatment failure, which would require an additional course of therapy.*

10.2. Disposition of Subjects and Baseline Comparisons

Summaries of all subjects screened, recruited, and enrolled will be provided, according to the CONSORT guidelines. The treatment groups will be evaluated at baseline with respect to demographics and baseline measurements related to efficacy and safety without formal statistical testing.

10.3. Analyses of Outcome Measures

The primary analysis will evaluate SVR-12 rates of HCV-negative lung transplant recipients who receive a lung from an HCV-infected donor and subsequently develop de-novo HCV. All patients will be assessed for toxicity and included in the safety analysis. This analysis will include summaries of the incidence and grade of toxicities. Patients will be evaluated for serious adverse events. Safety interim analyses will be performed and reported at each DSMB meeting.

10.4. Missing Data and Dropouts

We will attempt to minimize missing data, however we have planned for its occurrence. For subjects lost to follow-up, we will use all of the information available until the end of follow-up. Subjects who withdraw consent will no longer be followed in this protocol. Patients will receive care from the patients' clinicians.

For patients lost to follow-up, we will use all the information available up to the time of loss to follow-up. For the primary end point, we will perform an analysis of completers only. We will also perform additional sensitivity analyses using imputation to assess the impact of missing data for the primary and secondary end points.

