Study observations	
 • Laboratory tests including hepatic function panel at screening and at multiple time points during follow-up. • Fibroscan at screening, post-transplant (prior to treating HCV), and post-treatment. • HCV RNA prior to treatment, on treatment, and 4 and 12 weeks after completing Zepatier, Epclusa, or another appropriate antiviral treatment.
Type of control	None
Number of subjects	Estimated 11 HCV-negative subjects transplanted with a lung from an HCV-infected donor
Plan for statistical analysis	Primary endpoint:

	
• Post-treatment sustained virologic response (SVR) 
Secondary endpoints:
 
• Determine if there are major adverse events attributable to HCV therapy in post-lung transplant patients.• Evaluate 1-year lung graft survival in HCV-negative patients who receive a lung transplant from an HCV-positive donor• Determine the rates of spontaneous HCV clearance among HCV-negative patients with lung failure receiving a lung from an HCV-positive donor 
Data analysis:
 
The primary analysis will be based on a calculation of SVR rates (number of subjects with SVR-12; negative HCV RNA 12 weeks after completing Zepatier, Epclusa, or another appropriate antiviral treatment / (number of subjects treated with Zepatier, Epclusa, or another appropriate antiviral treatment post-lung transplantation)

--	---

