8 CHAPTER 5: DATA COLLECTION

8.1. Study visits

Study visits are scheduled to occur following subjects' standard post-transplant follow-up visits. Since treating cardiologists do not always require stable post-transplant patients to attend these visits, subjects may be asked to come in solely for study visits. These visits will be encouraged, but not required unless the study drug is being dispensed that day. For all other study visits, a missed visit by a stable subject who has had necessary labs drawn will not be considered a protocol violation.

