8.1.3.8. Visits 8 & 9: Post-Lung Transplant (day 84 ±7, day 112 ±14)

Visit #8 should occur 12 weeks (84 ±7) after the subject's lung transplant and will coincide with the subject's regularly scheduled post-transplant follow-up visit. Visit #9 should occur 16 weeks (112 ±14) after the subject's lung transplant and will immediately follow the subject's regularly scheduled post-transplant follow-up visit.

Midway between these study visits, subjects will be phoned in order to ensure drug adherence, if necessary

For both visits, the staff will call the subject 1-2 days before the visit to remind subject of visit. During this phone call, the research staff will remind the subject where to go for the study visit, to take their routine and study medications as they usually would prior to the visits and, if a fibroscan is needed, inform the subject and remind him/her to not eat or drink for three hours before the study visit.

The following procedures and activities will be performed:

- Assess for Adverse Events
- Obtain medication data
- Research Phlebotomy (See Section 8.2.1 for complete list)
 - Note: Timing for HCV RNA viral load, post treatment, should, as best possible, follow the important data collection points post treatment. These are as follows:
 - Post-treatment: This should occur after the subject has completed treatment of the study drug.
 - SVR 4: This should occur ~4 weeks after the subject has completed treatment.
 - SVR 8: This should occur ~ 8 weeks after the subject has completed treatment.
 - SVR 12: This should occur ~12 weeks after the subject has completed treatment.
 - SVR 24: This should occur ~24 weeks after the subject has completed treatment.
- Fibroscan (elastography of liver) for one visit only
- Health Status Questionnaire (RAND-36) (to assess changes in health status from pre- to post-transplant)
- Pill count and verbal assessment for drug adherence
- Replenish study drug
 - Note: The staff will replenish the subject's supply of the Zepatier or Epclusa or another appropriate antiviral therapy between visits 7 & 8, if necessary. This is based on management of patients NS5A resistance variants, in any were are present. The staff will also remind the subject how to take the medication, for those subjects still on study medication.

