9.2.2. Graft Survival

Graft survival will be based on standardize United Network for Organ Sharing (UNOS) criteria, with a graft failure defined as subject death, or re-transplantation within the first year post-transplantation.

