10.5. Protocol Violations

Serious protocol deviations such as discontinuation of experimental treatment unrelated to adverse events (AEs) will be carefully recorded and regularly reviewed by co-Principal Investigators. Remedial changes in procedure will be recommended where feasible to reduce the incidence of such deviations. The causes and circumstances of all violations will be documented where known for purposes of future secondary analyses and interpretation. Because all primary analyses will be intent-to-treat, it is essential that violations be kept to a minimum, especially where it is possible to influence their rate of occurrence. A missed study visit will not be considered a protocol violation unless the study drug was scheduled to be dispensed at the visit, the subject did not have necessary labs done, or the subject has not been stable.

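### Section 10.4 plans a completers-only analysis of the primary end point, with no definition or label, against the synopsis formula (all treated) and the intent-to-treat rule in section 10.5

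*Combined protocol and SAP*

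**What the plan says.** Four places bear on how the primary rate is formed.

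- **Synopsis, Data analysis.** The primary analysis is a ratio: subjects with SVR-12 over the "number of subjects treated with Zepatier, Epclusa, or another appropriate antiviral treatment post-lung transplantation". The denominator has no completer restriction.
- **Section 10.3.** The primary analysis concerns recipients who develop de-novo HCV, again with no completer restriction.
- **Section 10.4.** "For the primary end point, we will perform an analysis of completers only". The next sentence reads: "We will also perform additional sensitivity analyses using imputation to assess the impact of missing data for the primary and secondary end points". No imputation method is named, and a completer is not defined here or elsewhere.
- **Section 10.5.** "Because all primary analyses will be intent-to-treat, it is essential that violations be kept to a minimum". Sections 8.3, 12.7 and 12.9 also arrange follow-up so that an intention-to-treat analysis is possible.

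Section 9.1.1 defines SVR-12 as undetectable HCV RNA 12 weeks after the last dose. Section 10.4 also states: "Subjects who withdraw consent will no longer be followed in this protocol". No section says explicitly how a treated subject with no SVR-12 result is counted in the primary analysis.

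**The concern.** Section 10.4 is the only place that deals with missing primary data, so an analyst who has a missing SVR-12 result will turn to it. Read alone, it points to a denominator that leaves such subjects out. The synopsis formula keeps them in the denominator and, since they have no negative HCV RNA, out of the numerator. The same data could therefore yield two different headline rates.

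Missing results are foreseeable. Section 10.4 itself provides for loss to follow-up and ends follow-up when consent is withdrawn, and section 12.7 warns that clinical events could leave endpoint data missing. Death before the SVR-12 time point would have the same effect.

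What is at stake is the reported estimate and its interval. Section 4.1 presents the pilot as the step before a funding application for a multicentre randomised trial, so the choice of primary rate should be fixed before the data are seen.

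**Working it through.** **Inputs.** Planned number treated: n = 11 (section 3). The documents give no dropout rate, death rate, target SVR rate or sample-size calculation, so there is no figure of the plan's own to reproduce. Assumed here: m = 0 to 3 treated subjects with no SVR-12 result, and f = 0 or 1 observed virologic failures.

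**Formulas.** Let x = n − m − f be the number with SVR-12.

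- Completer rate, taking a completer as a treated subject with an SVR-12 result: x/(n − m).
- Synopsis rate: x/n.
- Exact (Clopper-Pearson) 95% limits for x of k: lower = 2.5% quantile of Beta(x, k − x + 1); upper = 97.5% quantile of Beta(x + 1, k − x). When x = k, the lower limit is 0.025^(1/k) and the upper limit is 100%.

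Since n − m ≤ n, x/(n − m) ≥ x/n, with equality when m = 0 (or when x = 0).

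**Every observed subject cured (f = 0)**

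| m | Completers | All treated | Gap (points) |
|---|---|---|---|
| 0 | 11/11 = 100% (71.5-100) | 11/11 = 100% (71.5-100) | 0 |
| 1 | 10/10 = 100% (69.2-100) | 10/11 = 90.9% (58.7-99.8) | 9.1 |
| 2 | 9/9 = 100% (66.4-100) | 9/11 = 81.8% (48.2-97.7) | 18.2 |
| 3 | 8/8 = 100% (63.1-100) | 8/11 = 72.7% (39.0-94.0) | 27.3 |

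**One observed failure (f = 1)**

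| m | Completers | All treated | Gap (points) |
|---|---|---|---|
| 0 | 10/11 = 90.9% (58.7-99.8) | 10/11 = 90.9% (58.7-99.8) | 0 |
| 1 | 9/10 = 90.0% (55.5-99.7) | 9/11 = 81.8% (48.2-97.7) | 8.2 |
| 2 | 8/9 = 88.9% (51.8-99.7) | 8/11 = 72.7% (39.0-94.0) | 16.2 |
| 3 | 7/8 = 87.5% (47.3-99.7) | 7/11 = 63.6% (30.8-89.1) | 23.9 |

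**Chance that the two rates differ.** With an assumed per-subject missingness d, P(at least one of 11 missing) = 1 − (1 − d)^11. For d = 5%, 10%, 15% and 20% this is 43%, 69%, 83% and 91%.

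**The definition matters too.** If a completer were someone who finished the drug course, a subject who stopped early but was sampled and cured would leave both numerator and denominator. With 10 of 11 cured, that gives 9/10 = 90.0% against 10/11 = 90.9%. The one-way direction above therefore depends on defining a completer by an observed SVR-12 result.

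**Later samples.** The plan schedules HCV RNA after the SVR-12 point ("SVR 24: This should occur ~24 weeks after the subject has completed treatment", and week 52) but does not say whether a later result may stand in for a missed one. Suppose 9 subjects are cured and 2 have no SVR-12 sample, one of whom is undetectable at week 36. The rate is then 9/9 = 100% in completers, 10/11 = 90.9% if the later result counts, and 9/11 = 81.8% if it does not.

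The week 36 draw falls late enough to be informative:

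- A start between day 2 and day 28 plus 84 days of drug puts the last dose at about day 86 to 112. The earliest week 36 draw is day 252 − 7 = 245. That is (245 − 112)/7 = 19.0 to (245 − 86)/7 = 22.7 weeks after the last dose.
- A 16-week course moves both the last dose and, under section 8.1.3.3.1, the procedures by 4 weeks, so the range is the same.

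**The case against.** The best reply is that the documents largely settle the matter. The synopsis states the primary analysis as an explicit formula, section 10.5 covers all primary analyses, and three further sections plan for intention-to-treat. The completers sentence stands under a missing-data heading, speaks of one analysis without calling it primary, and is followed by a reference to additional sensitivity analyses. This makes completers-as-supplementary the most coherent reading. It is never stated, however, and the word additional fits equally well if completers is the main analysis and imputation the supplement.

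The reply also limits the consequence, and this part stands. All the missing counts are assumed; 3 of 11 is already 27% missing. Section 10.2 promises disposition summaries, so a reader given the counts could recompute either rate.

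Two stronger inferences about missing results should be resisted. Section 8.1 says of study visits: "These visits will be encouraged, but not required unless the study drug is being dispensed that day". A reader might infer that SVR-12 results will often be absent. But the same section excuses a missed visit only for a stable subject whose necessary labs were drawn, section 10.5 does not excuse a missed visit without them, and SVR-12 is a lab result. Likewise, section 9.2.2 has "graft failure defined as subject death, or re-transplantation within the first year post-transplantation". That makes death a graft outcome over a year; it says nothing about how many deaths would precede the SVR-12 sample. Section 10.4 on withdrawal and loss to follow-up, with the warning in section 12.7, is the firmer support.

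**Conclusion.** The point holds as an unresolved conflict about the primary analysis set. A stated rule in section 10.4, if applied as primary, departs from the plan's own formula. With a completer defined as a subject with an observed SVR-12 result, the departure can only raise the rate. In the assumed cases with 1 to 3 of 11 missing, the difference is 8.2 to 27.3 percentage points; with none missing it is zero.

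A reader might infer that the plan has adopted completers as its primary analysis, or that the trial's conclusion is at risk. The documents support neither. Their weight favours all treated, and a single-arm pilot with no target rate or test has no decision that the choice could reverse. What remains is a headline estimate and interval that the plan does not pin down. This should be corrected before the data are seen.

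**What to change.** In section 10.4, replace the completers sentence with wording such as:

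> The primary SVR-12 rate is the number of subjects with SVR-12 divided by all subjects treated, with an exact 95% confidence interval; a treated subject with no SVR-12 result counts as not achieving SVR-12. Subjects who stop drug early but are sampled are analysed as observed. The completer analysis (treated subjects with an observed SVR-12 result) is a sensitivity analysis.

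For the imputation analysis already promised, specify best-case and worst-case bounds; for the primary end point the worst case equals the primary rate. Align sections 1, 10.3, 10.4 and 10.5 with this text. Classification by a later scheduled HCV RNA (week 36 or week 52) may be added as a further sensitivity analysis. It should stay out of the primary definition, because section 9.1.1 fixes the end point at 12 weeks after the last dose.

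The change is to wording only; it needs no extra subjects, visits or samples. Its downside is that, when results are missing, the reported rate will be lower than in completers and may understate virologic cure. The completer and best-case analyses show by how much.

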10.5. Protocol Violations

Serious protocol deviations such as discontinuation of experimental treatment unrelated to adverse events (AEs) will be carefully recorded and regularly reviewed by co-Principal Investigators. Remedial changes in procedure will be recommended where feasible to reduce the incidence of such deviations. The causes and circumstances of all violations will be documented where known for purposes of future secondary analyses and interpretation. Because all primary analyses will be intent-to-treat, it is essential that violations be kept to a minimum, especially where it is possible to influence their rate of occurrence. A missed study visit will not be considered a protocol violation unless the study drug was scheduled to be dispensed at the visit, the subject did not have necessary labs done, or the subject has not been stable.

10.6. Safety Analysis

All patients will be assessed for toxicity and included in the safety analysis. This analysis will include summaries of the incidence and grade of toxicities. Safety interim analyses will be performed at days 14, 30, 60, 90, 118, and 184, and will be reported at each DSMB meeting. SAEs will be evaluated by the DSMB.

11 CHAPTER 8: QUALITY CONTROL AND DATA HANDLING

11.1. Personnel Training

Prior to enrolling the first subject in the study protocol, the Principal Investigators will ensure that the Investigator staff has completed appropriate training and that all documentation including IRB approval is completed and available. The purpose of training is to ensure that study personnel are carrying out the protocol in a consistent way and adhering to good clinical practice guidelines. Staff will have current Human Subjects

Training Certification on file. Before enrollment begins, study staff who will perform the outcome assessments will be trained in all procedures, including completion of the REDCap database.

The co-PIs and research staff will constitute the first line of monitoring of the safety of the human participants. Surveillance for AEs will consist of questioning subjects about potential AEs at every study contact, having subjects report any AE to the study team, and having subjects undergo vital sign checks and physical exams during each study visit. Laboratories will be performed at selected visits and checked.

All study personnel are required to read the consent form, the protocol, and the IB.

11.2. Data Quality

The co-PIs and research staff will perform continuous monitoring of data quality and completion of CRFs. All consent forms and screening logs will be subject to audit by the University of Pennsylvania. Summary statistics from the screening logs will be sent to Merck quarterly or as requested. Finally, Merck staff reviews the reporting, documentation and follow-up of SAEs to assure that these events were handled according to required study procedures. All data on AEs and SAEs will be made available to the DSMB, as per the timeline outlined in the DSMB Charter.

11.3. Audit and Inspection

Inspections may be carried out by regulatory health authority representatives [i.e., FDA] as well as the IRB.

11.4. Archiving

Essential documents shall be archived safely and securely in such a way that ensures that they are readily available upon authorities' request. Patient (hospital) files will be archived according to local regulations and in accordance with the maximum period of time permitted by the hospital, institution or private practice.

12 CHAPTER 9: PARTICIPANT SAFETY AND CONFIDENTIALITY

12.1. Informed Consent

Informed Consent will be obtained for enrollment from participants. For each consent process, study personnel will discuss the details of the study, the risks and benefits, and the subject's rights and responsibilities if they choose to participate in the trial and their right to refuse to participate. It will be made clear that their clinical care will not be affected by their decision.

Each subject will have ample time and opportunity to ask questions and will be informed about the right to withdraw from the study at any time without any disadvantage and without having to provide reasons for this decision.

Only after the subject consents voluntarily and agrees to sign the ICF and has done so, may he/she enter the study. Additionally, the investigator and other information provider (if any) will sign and date the form. The subject will receive a copy of the signed and dated form.

The signed informed consent statement is to remain in the investigator site file or

If the patient is not capable of providing a signature, a verbal statement of consent can also be given in the presence of an impartial witness (independent of the investigator). This is to be documented by a signature from the informing physician as well as by a signature from the witness.

The ICF and any other written information provided to subjects / legal representatives or proxy consenters will be revised whenever important new information becomes available that may be relevant to the subject's consent, or there is an amendment to the protocol that necessitates a change to the content of the subject information and / or the written ICF. The investigator will inform the subject / legal representative or proxy consenter of changes in a timely manner and will ask the subject to confirm his/her participation in the study by signing the revised ICF. Any revised written ICF and written information must receive the IEC/IRB's approval in advance of use.

12.2. Institutional Review Board Process

Study staff will obtain IRB approval before any study procedures are initiated.

12.3. Insurance

The lung transplant itself will be paid for by subjects' insurance carriers, and does not require any additional pre-authorization because of the potential to receive a lung from a hepatitis C-positive donor. The costs of all visits and tests described above will be billed to the insurance carrier, except for: 1) the blood draw for research purposes (which includes the hepatitis C genotype test, which is based on a laboratory-developed test using materials purchased from the commercial entity that developed this test, and will be paid for by the research team), and 2) the study drug Zepatier in the event of infections with genotype 1 or genotype 4 HCV, which will be provided by Merck, and 3) other antiviral therapies for infections with HCV that are neither genotype 1 nor genotype 4; these therapies will be provided by HUP until such time that the subject's insurance provides coverage for the drug. In the event that the subject's insurance denies coverage for the treatment, HUP will provide the full course of appropriate HCV therapy as well as a second treatment course of antiviral therapy for HCV if the first treatment fails.

Subjects are still responsible for any deductibles or applicable co-pays for routine office visits, blood work and procedures. We do not expect subjects to have health insurance coverage/payment issues due to becoming infected with hepatitis C, per se, and the study is designed so subjects do not require additional study visits post-transplant, provided there are no adverse events.

12.4. Laboratory Values

The following clinical laboratory tests will be measured and repeated at time points specified in schedule of procedures (section 8.2.1) and as clinically indicated.

